**CCI**

Amendment 2.0 describes an amendment to the Statistical Analysis Plan for Protocol A5481122, Amendment 1.0 (dated April 4, 2019). The changes to Amendment 1.0 can be identified by using the Track Changes option in Word.

Amendment 3.0 is prepared after the Flatiron Analysis Database transferred and locked. Primary and most secondary analysis had been already performed except detailed updates the analyses of treatment patterns in terms of initial dose, dose adjustment, time to treatment discontinuation, time to next line of therapy, and time to chemotherapy. It also examines the associations of initial Palbociclib dose (125mg, 100/75mg) with demographic and clinical characteristics, time to treatment discontinuation, real world PFS, real world tumour response, and OS if sample size is large enough for meaningful statistical analyses.

Text copied directly from Protocol A5481122 is italicized.

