## 2.1 STUDY DESIGN

**Study design:** *This is a retrospective cohort study utilizing data derived from the Flatiron Health Analytic Database to describe patient characteristics and effectiveness of Palbociclib + Letrozole and Letrozole alone as first line therapy in HR+/HER2- MBC during the period of February 3/2015 through 3 months prior to the data cutoff date of the current Flatiron data release in the US real-world clinical practice setting.*

- **Index date:** the start date of the first line therapy for Palbociclib + Letrozole or Letrozole alone between February 3, 2015 and 3 months prior to the cutoff date of the current data release. Index dates will be restricted to a date chosen to allow a potential duration of treatment of at least 3 months for all patients.
- **Observation period:** February 3, 2015 through the cutoff date of the current data release.
- **Follow-up:** Patients will be followed from the index date to the data cutoff date, or death, whichever came first.

**Data source:** *Flatiron Health's longitudinal, demographically and geographically diverse database is derived from electronic health record (EHR) data from over 265 cancer clinics (~800 sites of care) including more than 2 million active US cancer patients.* The analysis will use the following data sets:

Data Set Name	Description
Demographics	Contains patient demographic information. Data set consists of one record per patient.
Visit	Contains information on all visits including the visit date, type of information (vitals, treatment, and/or lab) collected during the visit. Data set consists of one record per patient per visit.
ECOG	Contains information about ECOG performance status including the ECOG date and value. Data set consists of one record per patient per ECOG record.

LineOfTherapy	Contains information about each line of therapy received by the patient, as defined by Flatiron business rules including the line number, line name, start and stop dates for the line. Data set consists of one record per patient per line of therapy.
Enhanced_Mortality_V2	Contains the month and year in which the patient died. The complete date is not provided due to patient confidentiality reasons. Data set consists of one record per patient for patients who died.
Enhanced_MetastaticBreast	Contains the initial diagnosis date and initial MBC date and the Stage at the initial diagnosis. Data set consists of one record per patient.

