#### **4.2 TREATMENT WITH A CDK4/6 INHIBITOR AS PART OF A CLINICAL TRIAL SUBGROUPS**

***Subgroup Analyses.*** *Analyses of study measures, as described above, may be repeated focusing alternatively on the following subgroups of interest—sample size permitting—which will be defined on the basis of:*

- Age (year)  
 $\leq 50$ , 51-64, 65-74, 75+
- Race  
White, Black/Asian/Hispanic/Latino
- Disease stage at initial diagnosis  
I or II, III, IV
- ECOG performance status  
0, 1 or 2,  $\geq 1$
- Site of metastasis  
Bone only, Visceral, Non-visceral
- # Metastatic sites

1, 2,  $\geq 3$

- Menopausal status
- ER/PR Status (all patients in data received from Flatiron are HR+)  
ER+/PR-, ER+PR+, ER-/PR+

**Sensitivity Analyses.** IPTW performed under Amendment I indicated an inability to adequately balance baseline variables and clinical characteristics. Propensity score matching (PSM) balanced the two cohorts, but on a reduced number of patients. Therefore, results using PSM and IPTW will be presented.

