Real-world PFS (rwPFS)	
Time in months from index date to progression or censoring date will be calculated.
 
Based on improved understanding of the PFS analysis in PALOMA-2 the following changes will be made to the PFS outcome definition.
 
Event: Any death or disease progression (concluded by the treating clinician based on radiology, laboratory evidence, pathology, or clinical assessment). If patients did not die or have disease progression, they were censored at the date of initiation of next line of therapy for patients with two or more lines of therapy or their last visit date during the study period for patients with only one line of therapy.

Real-world tumor responses (rwTR)	
 
● Complete response: complete resolution of all visible disease.
 
● Partial response: partial reduction in size of visible disease in some or all areas without any areas of increase in visible disease.
 
● Stable disease: no change in overall size of visible disease; also included cases where some lesions increased in size and some lesions decreased in size
 
● Progressive disease: an increase in visible disease and/or presence of any new lesions; included cases where the clinician indicated progressive disease.
 

Response rate	
 
● Complete response or partial response divided by the number of patients with at least one tumor assessment while on the index treatment.
 

Time to next line of anti-cancer therapy	
 
● Defined as the time from the initiation of 1LOT (PAL+AI) until either 
 
○ the day before the start of 2LOT for patients with evidence of 2LOT, or
 
○ death if the death occurred within 60 days following the patient's last administration of 1LOT (PalB/AI)
 
○ Whichever occurred first.
 
 
 
● If a patient did not have evidence of 2LOT and did not die within the 60 days following the last 1LOT administration, the patient was censored at the latest available date that occurred on or before the end of study date of either last drug administration plus the number of days in a treatment cycle (last PAL/AI administration + 28 days) last visit date (e.g., office visit, lab, radiology, etc), or data cutoff date.
 

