## 6 STATISTICAL METHODOLOGY AND STATISTICAL ANALYSES

This analysis will compare effectiveness outcomes of real-world progression-free survival (rwPFS) as primary outcome and Overall survival (OS) tumor response and time to next line of anti-cancer therapy/chemotherapy as secondary outcomes (depending on the availabilities of the data) in female patients treated with Palbociclib + Letrozole as first line MBC therapy versus Letrozole alone.

Means, medians, and standard deviations will be provided for continuous variables. Counts and percentages will be provided for dichotomous and polychotomous variables. Appropriate tests (t-tests and chi-square tests) will be provided for baseline demographic and clinical characteristics.

Inverse probability treatment weighting (IPTW) will be used to balance baseline demographic and clinical characteristics and to adjust analyses for differences in observed potential confounders between the two study cohorts. The balance in important prognostic baseline characteristics will be assessed using a standardized differences approach, with values  $\geq 0.10$  indicating a non-negligible imbalance.

Propensity scores for use in IPTW will be calculated using a multivariable logistic regression model based on the following proposed baseline covariates such as age, race, practice type, type of MBC, ECOG performance score, disease stage at diagnosis (I–IV or unknown/undocumented), number of disease sites at MBC diagnosis (1, 2,  $\geq 3$ ), bone-only metastases, visceral metastases, and individual Charlson comorbidities, depending on data availability. Stabilized weights based on the propensity scores will be computed. The final list of variables to be used in the propensity score model will be discussed and determined during analysis development, after reviewing pre-matched descriptive tables. The selection of covariates for analysis will be based on the study team's clinical judgment.

The Kaplan-Meier method adjusted for weighted stabilized IPTW scores and 95% confidence intervals (CIs) will be used to estimate median rwPFS. Cox proportional hazards analyses adjusted for weighted stabilized IPTW scores will be used to estimate hazard ratios and 95% CIs for PFS.

The Kaplan-Meier method and 95% CIs will be used to estimate:

- proportions of patients surviving by cohort at follow-up years 1 through 4.

The Kaplan-Meier method adjusted for weighted stabilized IPTW scores and 95% CIs will be used to estimate:

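### As worded, rwPFS censoring at next-line start depends on whether the patient later progresses or dies

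*SAP*

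**What the plan says.** SAP 5.1 defines the rwPFS event with no limit of time or line: "Event: Any death or disease progression", as concluded by the treating clinician. The censoring sentence then reads "If patients did not die or have disease progression, they were censored at the date of initiation of next line of therapy", and this date applies "for patients with two or more lines of therapy". Event-free patients with a single line are censored at their last visit. Protocol Table 1 (section 9.3) carries the same rule. Its first-occurrence clause ranks death against progression and does not rank either against next-line start.

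SAP 6 sets "real-world progression-free survival (rwPFS) as primary outcome" of the palbociclib plus letrozole versus letrozole comparison. For two other endpoints SAP 5.1 does restrict deaths. Time to treatment discontinuation counts a death only during first line, and time to next therapy counts it only within 60 days of the last first-line administration. The note on Amendment 3.0 in SAP section 1 records the timing: "Primary and most secondary analysis had been already performed".

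**The concern.** The condition for censoring at the switch is that the patient never progresses or dies. Whether she leaves the risk set at the switch is therefore settled by what happens after it. Kaplan-Meier and Cox estimates need censoring at a given time to carry no information about later failure. Here it carries that information by construction, because after a progression-free switch only future failures remain at risk.

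The rule itself foresees such patients, since it assigns a censoring date to event-free patients with two or more lines. If it is applied literally, rwPFS is understated in any cohort with switching, and the hazard ratio for the primary outcome is distorted when the cohorts switch at different rates.

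**Working it through.** **1. The wording applied to two patients.** Both start a next line without progression at month 8, and both reach cut-off after month 26.

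| | Patient A | Patient B |
|---|---|---|
| After the switch | Progresses at month 26 | No event by cut-off |
| Rule as worded | Event at 26 | Censored at 8 |
| Rule (a): every event-free switcher censored at the switch | Censored at 8 | Censored at 8 |
| Rule (b): switch ignored | Event at 26 | Censored at last visit |

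Nothing distinguishes the two between months 8 and 26, but under the wording only A is at risk then.

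**2. The plan's own figure.** SAP 3.3 gives medians of 14.5 and 24.8 months, two-sided alpha 0.05, 90% power and 138 patients per group. If survival is exponential, HR = 14.5/24.8 = 0.585. Schoenfeld events = 4(1.960 + 1.282)²/(ln 0.585)² = 146. The event probability is p = 1 − e^(−λf)(1 − e^(−λA))/(λA). With uniform accrual (assumed) over A = 40.2 months and f = 3 months, p is 0.615 and 0.448, mean 0.531. Then 146/(2 × 0.531) = 137.4, or 138 per group. The figure reproduces, and the wording problem does not touch it.

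**3. How far the literal rule inflates the hazard.** Let P(t) be the probability of having switched by t. Let q(t) be the probability that a patient still event-free and under observation at t fails before cut-off. The number of events at t is right, but the risk set is only 1 − P(t)[1 − q(t)] of its proper size. With switching unrelated to prognosis, the apparent hazard is λ / {1 − P(t)[1 − q(t)]}.

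Take palbociclib at month 24:
- λ = ln 2/24.8 = 0.02795 per month.
- Assumed switching is 10% per year from month 2, a monthly rate of −ln(0.9)/12 = 0.00878. So P = 1 − exp(−0.00878 × 22) = 0.176.
- Cut-off is uniform from 3 to 45.9 months after index (42.9 months from 3 February 2015 to 31 August 2018, plus 3), which leaves 21.9 months. So q = 1 − [1 − exp(−0.02795 × 21.9)]/(0.02795 × 21.9) = 0.252.
- Inflation = 1/(1 − 0.176 × 0.748) = 1.15.

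For letrozole λ = ln 2/14.5 = 0.0478, q = 0.380, and the inflation is 1/(1 − 0.176 × 0.620) = 1.12. Integrating the inflated hazards gives medians of 23.4 and 14.2 months.

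**4. Simulation of the literal rule.** There were 1,000,000 patients per cohort, with the same medians and cut-off, monthly visits, and 10% of first events being deaths without recorded progression. Switching rates are assumptions. L is letrozole, P is palbociclib plus letrozole.

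| Switching per year, L / P | Median L | Median P | HR | Events after next-line start, L / P |
|---|---|---|---|---|
| 2% / 2% | 14.4 | 24.5 | 0.585 | 1.5% / 1.7% |
| 5% / 5% | 14.3 | 24.0 | 0.587 | 3.6% / 4.3% |
| 10% / 10% | 14.2 | 23.4 | 0.591 | 7.2% / 8.5% |
| 20% / 20% | 13.9 | 22.1 | 0.599 | 13.9% / 16.4% |
| 10% / 5% | 14.2 | 24.0 | 0.572 | 7.2% / 4.3% |
| 5% / 10% | 14.3 | 23.4 | 0.609 | 3.6% / 8.5% |
| 20% / 10% | 13.9 | 23.4 | 0.564 | 13.9% / 8.5% |
| 10% / 20% | 14.2 | 22.1 | 0.631 | 7.2% / 16.4% |

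Medians and event shares in the unequal rows are carried over from the equal-rate runs. Repeat runs gave 0.628 and about 0.635 in the last row, so the third decimal should not be pressed. Rules (a) and (b) both return medians of 14.4–14.5 and 24.7–24.8 and HR 0.583–0.587 throughout. In a simpler run with no true difference (both medians 14.5), switching of 0.02 against 0.01 per month gives HR 0.95 or 1.05 under the literal rule, and about 1.00 under (a) or (b).

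**5. In standard errors.** With 650 per cohort (SAP 3.3, unweighted) the SE of log HR is 0.077. Then ln(0.564/0.585)/0.077 = −0.5 and ln(0.631/0.585)/0.077 = 1.0. SAP 4.2 says "Propensity score matching (PSM) balanced the two cohorts, but on a reduced number of patients" without giving the number. At an assumed 300 per cohort the SE is 0.113, and the shifts are −0.3 and 0.7.

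**6. If switchers have a worse prognosis.** A gamma frailty of variance 0.5 was shared by event and switch times. At 10% per year in both cohorts, the palbociclib median is 23.6 under the wording, 25.8 under (a) and 24.7 under (b), against 24.8. With unequal switching and a no-switch HR of about 0.64:

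| Switching, L / P | As worded | (a) | (b) |
|---|---|---|---|
| 10% / 20% | 0.669 | 0.622 | 0.641 |
| 20% / 10% | 0.632 | 0.649 | 0.641 |

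**The case against.** The strongest reply is that the sentence is shorthand for patients without progression or death before the next line, and that the programmed rule, or the data vendor's business rules to which SAP 5.1 refers, already works that way. That is possible and cannot be excluded from the documents. But neither document says it. The same SAP table restricts deaths where a restriction was meant, and the rwPFS row was deliberately revised, so a programmer could reasonably take it at face value.

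The second reply is that progression-free switching may be rare. The line rules in SAP 5.1, written for time to discontinuation, say that an exchange between aromatase inhibitors or between CDK4/6 inhibitors without progression does not start a second line. Other additions after 60 days still can. No rate is given, so this stands as a limit on the size of the problem.

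The third reply is that censoring every switcher is not a clean remedy. This stands. Step 6 shows that (a) can err about as much as the current wording, in the opposite direction.

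A reader might infer that the reported rwPFS result is biased, or biased in favour of palbociclib. The documents support neither. They do not say how late events were handled, and they give no switching rate for either cohort.

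**Conclusion.** The defect is in the stated rule for the primary outcome and should be fixed. As worded, censoring at a progression-free switch depends on later outcome. Harm follows only if the rule was applied literally and such switches occur. Under those conditions the medians are shortened. The hazard ratio moves little at equal switching (0.585 to 0.599 even at 20% per year) and by up to about one standard error in the unequal scenarios tried. No scenario built on the SAP medians brings it near 1.

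All of these sizes rest on assumed switching rates, exponential survival and, except in step 6, switching unrelated to prognosis. Confidence is medium, because the wording is clear but the practice is unknown.

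**What to change.** First, state how progressions and deaths after next-line start were handled in the analysis already performed. If they were excluded, correct only the wording. If they were counted, label the change post hoc and show the existing and corrected results together.

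Then put one rule, applied to every patient whatever happens later, in both SAP 5.1 and Protocol Table 1:
- **(a)** A progression or death counts only if it falls on or before next-line start, and every patient who starts a next line without earlier progression is censored at that start; or
- **(b)** Next-line start is ignored, every progression and death counts, and event-free patients are censored at last visit whether or not a next line began.

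Name one as the main analysis and report the other beside it. Neither is free of cost. Rule (a) loses events: at 10% switching per year, about 648 instead of 703 per 1,300 patients, which widens the standard error by √(703/648) = 1.04. It is also biased if switchers differ in prognosis, and it drops progressions written up just after a switch. Rule (b) includes the effect of later therapy and depends on progression being recorded after the switch.

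Report by cohort the number of events after next-line start, and how many fall within, say, 30 days of it. The last column of the table in step 4 gives a scale for reading these counts.

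For patients with one line, report the number of deaths long after the last visit. They count as events while survivors are censored at that visit, which is a smaller form of the same problem. With an assumed 5–10% per year lost to follow-up it moves the palbociclib median only to 24.5–24.4. Cutting deaths off at the last visit is not the cure: it would raise that median to 27.6 if 10% of first events are deaths.

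The mortality file "Contains the month and year in which the patient died" only. Under (a), a death in a patient with a next line should therefore be placed after that start as a matter of fact, not by an imputed day.

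The work is a short text change in each document and a rerun on data already held, since the line-of-therapy file describes each line "as defined by Flatiron business rules including the line number, line name, start and stop dates for the line".

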| Real-world tumor responses (rwTR) | Real-world tumor responses are assessed based on treating clinician's assessment of radiological evidence for change in burden of disease over the course of treatment: 
 • Complete response: complete resolution of all visible disease. • Partial response: partial reduction in size of visible disease in some or all areas without any areas of increase in visible disease. • Stable disease: no change in overall size of visible disease; also included cases where some lesions increased in size and some lesions decreased in size. • Progressive disease: an increase in visible disease and/or presence of any new lesions; included cases where the clinician indicated progressive disease. |
| Response rate | Complete response or partial response divided by the number of patients with at least one tumor assessment while on the index treatment |

| | |
|--|--|
| Real-world duration of treatment (rwDOT) | Months from index treatment initiation to end of the treatment |
| Time to next line of anti-cancer therapy | Months from index treatment initiation to next line of anti-cancer therapy or death from any cause, whichever occurred first |
| Time to chemotherapy | Months from index treatment initiation to first use of chemotherapy or death from any cause, whichever occurred first |

Table 2. List of Medications for the Treatment of HR+/HER2- Metastatic Breast Cancer

| Drug Name | Brand Name | Type of therapy | Code |
|-------------------|------------|-----------------|--|
| Anastrozole | Arimidex | Endocrine | S0170 |
| Exemestane | Aromasin | Endocrine | S0156 |
| Fulvestrant | Faslodex | Endocrine | J9395 |
| Letrozole | Femara | Endocrine | N/A |
| Megestrol acetate | Megace | Endocrine | S0179 |
| Raloxifene | Evista | Endocrine | N/A |
| Tamoxifen | Nolvadex | Endocrine | G8376, G8380, G8381, S0187 |
| Toremifene | Fareston | Endocrine | N/A |
| Everolimus | Afinitor | Target therapy | J7527, J8561 |
| Palbociclib | Ibrance | Target therapy | N/A |
| Ribociclib | Kisqali | Target therapy | N/A |
| Abemaciclib | Verzenio | Target therapy | N/A |
| Capecitabine | Xeloda | Chemotherapy | J8520, J8521 |

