Time to treatment discontinuation	
 
The time from the start of a treatment to the time of treatment discontinuation for any reason in 1LOT
 
Start date: PAL/AI start date in 1LOT
 
End date: 
 
A. PAL/AI end date in 1LOT
 
B. 2LOT start date
 
C. Death date in 1LOT
 
D. Whichever came first
 
 
 
Censoring date: latest available drug administration or latest visit/activity date (lab, office, radiology, etc), end of study, or loss to follow-up, whichever came first.
 
2LOT start date 
 
A. Start date of adding any new anti-neoplastic (chemotherapy, target therapy (eg., Abemaciclib, Ribociclib), or endocrine therapy) if there is evidence of disease progression or after 60 days of index date if there is no evidence of disease progression.
 
B. AI discontinuation or exchange from one AI to another AI is not considered as 2LOT start if there is no evidence of disease progression
 
C. Exchange from one PAL to another CDK4/6i AI is not considered as 2LOT start if there is no evidence of disease progression.
 
D. 1LOT was not advanced if PAL and/or AI were paused or stopped and then restarted within 120. Different days (90, 120, and 180) will be used as sensitivity analyses.
 
 
 

Organ-level metastatic sites	Number of sites; Sites of metastases (bone, lung, liver, brain, distant lymph nodes, other) Visceral vs. non-visceral, bone only
Modified Charlson comorbidity index (CCI)	As defined in the Flatiron database
Effectiveness outcomes	
Overall survival (OS)	
Time in months from index date to death due to any cause or censoring date will be calculated.
 
Based on an improved understanding of the death information in Flatiron and a better understanding of the OS analysis in PALOMA-2 the following changes will be made to the OS outcome definition.
 
Event: Any death recorded by Flatiron in the data extract. Patients who did not die will be censored at the time of data cutoff.

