Time to chemotherapy	
 
Defined as the time from the initiation of 1LOT PAL+AI until either 
 
The day before the start of subsequent chemotherapy for patients with evidence of chemotherapy, or
 
Death for any reasons
 
Whichever came first
 
 
 
If a patient did not have evidence of subsequent chemotherapy and did not die, the patient was censored 
 
at the last visit date (e.g, office visit, lab, radiology), or
 
data cutoff date
 
whichever came later
 
 
 

Initial dose of Palbociclib	
 
Index dose level of Palbociclib: 125mg, 100mg, or 75 mg
 

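### Time to next line drops deaths more than 60 days after the last first-line administration, which the protocol counts; the time-to-chemotherapy censoring rule can only return the data cutoff

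*SAP*

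**What the plan says.** **Time to next line.** Protocol 9.3, Table 1 defines it as "Months from index treatment initiation to next line of anti-cancer therapy or death from any cause, whichever occurred first". SAP 5.1 keeps the name but counts "death if the death occurred within 60 days following the patient's last administration of 1LOT". For patients with neither a second line nor such a death, "the patient was censored at the latest available date that occurred on or before the end of study date of either last drug administration" plus 28 days, last visit or data cutoff.

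**Time to chemotherapy.** Protocol Table 1 counts chemotherapy or death from any cause and gives no censoring rule. SAP 5.1 agrees on death ("Death for any reasons") and censors everyone else at last visit or data cutoff, "whichever came later".

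**Neighbouring rules.** The same SAP table censors time to treatment discontinuation at "latest available drug administration or latest visit/activity date (lab, office, radiology, etc), end of study, or loss to follow-up, whichever came first", and rwPFS at last visit for patients with one line of therapy. OS is censored at cutoff. SAP 2.1 on follow-up: "Patients will be followed from the index date to the data cutoff date, or death, whichever came first".

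**Role.** Both endpoints serve a secondary objective (Protocol 8). SAP 6 lists them as secondary outcomes, subject to data availability. SAP 6.1 says they are not intended as effectiveness measures.

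**The concern.** The protocol and SAP define different quantities under the name time to next line. The SAP explains why it changed the OS and rwPFS definitions but gives no reason here. Protocol 9.7 says that the methods for the primary and secondary objectives are in the protocol itself, so its definition still stands. Within the SAP, one late death without second line or chemotherapy is an event for time to chemotherapy and a censored time for time to next line.

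For time to chemotherapy, the last-visit option never operates. Chemotherapy is seen only in the health record, so a living patient who has left it is carried as chemotherapy-free to cutoff. At stake are the medians and landmark estimates of two secondary endpoints; the rwPFS and OS event and censoring rules are separate.

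**Working it through.** The documents give no event count, loss rate or expected median for these endpoints, so there is no plan figure to reproduce. The definitions settle what is wrong. The sizes below are illustrations on assumed inputs.

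**1. Time to next line.** Take a patient who stops first line, starts no second line and dies 90 days after the last administration. Protocol: event at death. SAP: 90 > 60, so censored.

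Constant-hazard check: if a share s of endings stops counting, the hazard falls to (1 − s) of its value and the median becomes 24/(1 − s).

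A simulation of 3 million patients assumed a true median of 24 months and no loss. In it, 10% of endings were deaths within 60 days of the last dose, a share s were deaths 60 to 180 days after it, and the rest were second line. Follow-up ended at death.

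| Late-death share s | 24/(1 − s) | Simulated median | Simulated 36-month estimate |
|---|---|---|---|
| 0% | 24.0 | 24.0 | 35% |
| 5% | 25.3 | 25.1 | 37% |
| 10% | 26.7 | 26.4 | 39% |
| 20% | 30.0 | 29.5 | 43% |

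Censoring the late death at death or at last activity before it changes these medians by no more than 0.1 month. With last-activity censoring and 10% annual loss, the 5% and 10% rows give 25.2 and 26.5.

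**2. Time to chemotherapy.** SAP 2.1 ends observation at the cutoff, so last visit ≤ cutoff and max(last visit, cutoff) = cutoff for every patient.

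Let c, d and l be the monthly hazards of chemotherapy, death and loss from the record, with every death captured. The SAP rule then estimates

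S(t) = exp(−dt) × [1 − c/(c + l) × (1 − exp(−(c + l)t))].

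Assume medians of 40 months to chemotherapy and 60 to death: c = ln 2/40 = 0.01733, d = ln 2/60 = 0.01155, and the true composite median is ln 2/(c + d) = 24.0. With 10% annual loss, l = −ln(0.9)/12 = 0.00878. At t = 25.9: 0.741 × [1 − 0.664 × (1 − 0.509)] = 0.50, so the estimated median is 25.9.

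| Medians, chemotherapy/death | No loss | 5% per year | 10% per year | 20% per year |
|---|---|---|---|---|
| 40/60 | 24.0 | 24.9 | 25.9 | 28.2 |
| 30/120 | 24.0 | 25.3 | 26.8 | 31.0 |
| 60/40 | 24.0 | 24.5 | 25.1 | 26.4 |

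For 40/60 the 36-month estimate is 35%, 37%, 39% and 43%. If only 91% of deaths are captured (the lung cancer figure in Protocol 9.8), the 40/60 medians are 25.3, 26.4, 27.5 and 30.4.

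**3. Is last-activity censoring better?** Simulated error in the median, in months, with index dates uniform over 42.9 months, cutoff 3 months later, visits every 28 or 84 days, all deaths counted, and patients active within 120 days of cutoff treated as followed to cutoff (120 is illustrative):

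| Medians, annual loss | SAP rule | Last activity with gap |
|---|---|---|
| 40/60, 5% | +0.9 | −0.4 |
| 40/60, 10% | +1.9 | −0.7 to −0.9 |
| 40/60, 20% | +4.2 | −1.5 to −1.8 |
| 60/40, 5% | +0.5 | −0.5 to −0.6 |
| 60/40, 10% | +1.1 | −1.0 to −1.2 |
| 60/40, 20% | +2.4 | −2.0 to −2.3 |

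The negative error arises because lost patients who die still count as events, while lost patients who survive leave the risk set. With 91% death capture, 60/40 and 5% loss, the errors are about +2.7 (SAP) and +0.65 to +0.80 (last activity). Without the gap provision, last-activity censoring can do worse than the SAP rule: −1.3 against +0.9 at 40/60, 5% loss and 84-day visits.

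**The case against.** The best defence concerns time to chemotherapy. The protocol sets no censoring rule for it, so cutoff censoring breaches nothing. It matches the study-wide follow-up definition and the OS rule, and the composite includes death, which is partly found from sources outside the record. All of that stands. A reader might also infer that last-activity censoring is simply more accurate. It is not: where deaths outnumber chemotherapy starts and all deaths are captured, the two rules err by about the same amount in opposite directions at 5% and 10% loss. The replacement also needs a gap length chosen after database lock.

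A 60-day window may have been intended for time to next line. It would then be a different endpoint and need its own name and rationale.

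Two further readings go too far. The first is that the time-to-next-line censoring sentence sends everyone to the cutoff. The wording permits this, but last activity capped at cutoff is at least as natural; the sentence is ambiguous. The second is that the window fails because of the mortality file ("Contains the month and year in which the patient died. The complete date is not provided due to patient confidentiality reasons"). The month-only date is a general matter that also touches OS and rwPFS, and the point does not rest on it.

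Finally, SAP 6.1 does not intend these outcomes as effectiveness measures, and no visible decision rule is specific to them. That limits the impact but does not reconcile the definitions.

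**Conclusion.** The time-to-next-line definition should be corrected. The SAP contradicts the protocol without explanation and turns some events into censored times. With assumed late-death shares of 5%, 10% and 20%, a 24-month median becomes about 25, 26 to 27, and 30; with no late deaths the definitions agree.

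The time-to-chemotherapy rule has an option that never operates, and it biases the curve upward if patients are lost or deaths are missed. The size is about 1 month at 5% annual loss and 2 months at 10% for 40/60 medians with complete death capture, and nil with no loss and complete capture. The documents give no loss rate, late-death share, event mix or death capture for this cohort, so the actual size is unknown. They do not support calling this rule a protocol breach, or its replacement uniformly better.

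**What to change.** 1. **Time to next line:** make death from any cause the event, as in the protocol. Keep the 60-day version, if wanted, only as a separately named sensitivity endpoint. Reword the censoring date as the later of last administration plus 28 days and last visit, limited by death and data cutoff.
2. **Time to chemotherapy:** censor event-free patients at last recorded activity with the cutoff as upper limit. Treat patients active within a stated, fixed gap before cutoff as followed to cutoff. Report the cutoff-censored version beside it; the difference shows how far the estimate depends on loss.
3. **Record:** SAP section 1 lists these analyses among those updated in Amendment 3.0, prepared after database lock. Date the change, state the gap length and its basis, and document both as made after lock.

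The cost is two rows of the SAP 5.1 table and a run or rerun of two analyses. Reported times may become somewhat shorter: time to next line if late deaths occurred, time to chemotherapy if patients were lost.
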